3.3. Number of Subjects

3.3.1. Sample Size

As this is an extension study, the sample size was based on the planned sample sizes of studies 997HA301 (N=144), 8HA02PED (N=50), 997HA307 (N=12), and 997HA309 (N=8, the subset of subjects from Australia and New Zealand only). This might be increased based upon enrollment being greater than expected in these studies.

3.3.2. Study Sample

Subject inclusion and exclusion criteria can be found in Sections 8.1 and 8.2 of the protocol.

3.3.3. Procedures for Discontinuing Treatment and Removal of Subjects from the Study

A subject *must* permanently discontinue rFVIII Fc for any of the following reasons:

- A Grade 2 or greater allergic drug reaction in association with administration of rFVIII Fc, as defined below by the Recommendations for Grading of Acute and Sub-Acute Toxic Effects on the World Health Organization WHO scale [[WHO handbook, 1979](#)]:
 - Grade 2 Bronchospasm related to rFVIII Fc; no parenteral therapy needed
 - Grade 3 Bronchospasm related to rFVIII Fc; parenteral therapy required
 - Grade 4 Anaphylaxis related to rFVIII Fc
- A high-titer inhibitor (≥ 5.00 BU/mL)
- Use of FVIII products other than rFVIII Fc, unless it occurs in 1 life-threatening emergency and/or as a result of 1 accidental use, and the Sponsor agrees to retain the subject in the study.
- Any condition a subject develops that precludes him from complying with the study procedures.
- The subject experiences a medical emergency that necessitates discontinuation of treatment.

- Clinical judgment of the Investigator: a subject may have treatment permanently discontinued, if in the opinion of the Investigator, it is not in the subject's best interest to continue with the study treatment.
- The parent or legal guardian can withdraw the subject from the study at will at any time.
- The subject and/or his parent/guardian withdraw consent.
- At the discretion of the Investigator or Sponsor for noncompliance

The reason for discontinuation of study treatment must be recorded in the subject's eCRF.

For any subject who no longer responds to treatment with rFVIII^{FC}, as determined by the Investigator, a decision will be made with the Sponsor whether to continue the subject on the study.

Subjects who discontinue treatment should remain in the study to complete protocol-required tests and assessments, and then must be permanently withdrawn from the study.

3.3.4. End of Study

The end of study is defined as the last subject's last visit. This will occur once all subjects have completed the study, discontinued prematurely, switched to commercially available rFVIII^{FC} when it becomes available in the applicable participating country, or switched to EAP (Expanded Access Program).

3.3.5. Randomization and Blinding

This is an open-label study with no blinding or randomization.

4. ANALYSIS POPULATIONS

For the purpose of the analysis, analysis populations will consist of subjects who enrolled into study 8HA01EXT from parent studies 997HA301, 8HA02PED, 997HA307, and 997HA309.

4.1. All-enrolled Analysis Set

All subjects who consent to participate in 8HA01EXT will be included in the All-enrolled Analysis Set.

4.2. Full Analysis Set (FAS)

Subjects who receive at least 1 dose of rFVIIIFc in study 8HA01EXT will be included in the Full Analysis Set (FAS). Analyses of efficacy will be performed on the FAS.

4.3. Safety Analysis Set

Subjects who receive at least 1 dose of rFVIIIFc in study 8HA01EXT will be included in the Safety Analysis Set.

4.4. Surgery Subgroup

Surgery subgroup is defined as subjects who have undergone major surgery or have major surgical/rehabilitation periods described in Section 5.3.3 during study 8HA01EXT.

5. DATA HANDLING

This study is being conducted under the sponsorship of Biogen. Data management is being performed under contract with Quintiles in collaboration with Bioverativ. Statistical analysis is being performed by Bioverativ, using SAS® version 9.3 or higher and, where appropriate, additional validated software. This statistical analysis plan (SAP) is based on protocol Version 3, dated 26 August 2013 and will detail analyses to be performed and summaries to be produced for the final Clinical Study Report (CSR).

5.1. General Principles

The following rules will be followed for all applicable analyses contained in this SAP, unless specified otherwise.

Because the subjects from studies 997HA301/997HA307/997HA309 and study 8HA02PED are in different age groups (i.e. ≥ 12 years of age for studies 997HA301/997HA307/997HA309 and < 12 years of age for study 8HA02PED) and may therefore have different safety and efficacy profiles, analyses will be performed separately for the groups of subjects from the parent study or parent studies combined, as described in the table below. Further, the table categories (i.e. age cohort, treatment regimen, etc) by type of analyses for each grouping are also detailed unless specified otherwise.

Groups of subjects from the parent study or parent studies combined	Categories by type of analyses
8HA02PED	Baseline/Concomitant therapy and procedures: Age cohort and overall; treatment regimen (including surgery subgroup) and overall Exposure: Age cohort and overall; treatment regimen and overall Efficacy: Age cohort; treatment regimen Patient-reported outcomes: Age cohort and overall; visit Compliance/surgery/Safety: Visit (if applicable)
997HA301 997HA301/997HA307/997HA309 combined	Baseline/Concomitant therapy and procedures: Treatment regimen (including surgery subgroup) and overall Exposure: Treatment regimen and overall Efficacy: Treatment regimen

	Patient-reported outcomes: Visit Compliance/surgery subgroup/Safety: Visit (if applicable)
Overall	Compliance/Surgery/Safety: Visit (if applicable)

Where treatment regimen (which is defined as treatment regimen in study 8HA01EXT) is:

- Tailored prophylaxis
- Weekly prophylaxis
- Personalized prophylaxis
- Episodic

Age cohort for subjects from study 8HA02PED is as reported for that study, namely:

- <6 years old
- 6 to <12 years old

Summaries of study 8HA01EXT data will be produced using standard summary statistics. Listings will also only include data from study 8HA01EXT and the treatment regimen associated with each data point, unless specified otherwise. Data collected at unscheduled visits will be included in the definition of the maximum and minimum post-baseline values.

Unless specified otherwise, for the purpose of analyses involving change from baseline during 8HA01EXT, baseline will be defined as the last non-missing measurement (that can be used for data analysis) taken prior to or on the date of 8HA01EXT study Study Day 1 (see Section 5.1.1 for a description of study days). Eligible subjects will be enrolled at End of Treatment (EOT) visit of their parent study (997HA301, 8HA02PED, 997HA307, or 997HA309), which will serve as the Baseline Visit for this extension study (Visit 1). Baseline visit assessments may have been repeated if there was a gap in study treatment (e.g. a gap of greater than 37 days following the EOT Visit for the previous study). Post-baseline values are defined as any assessment taken after 8HA01EXT Study Day 1 (see Section 5.1.1 for a description of study days). In the case of unscheduled visits being taken for the same visit number assigned, the latest available non-missing assessment for that visit will be used for by-visit summaries.

Data collected at the local laboratories will be excluded from the analyses of laboratory data but will be included in the data listing.

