Treatment will be administered as tailored prophylaxis, weekly prophylaxis, personalized prophylaxis, or as an on-demand regimen. Subjects 12 years of age or older will be able to switch from one regimen to another at scheduled or unscheduled visits during the study, per Investigator discretion. Subjects less than 12 years of age will receive 1 of 2 prophylactic regimens, tailored or personalized, and will not have the option to change to a weekly prophylactic or on-demand regimen, unless they reach the age of 12 years during the study, at which time they can use any of the 4 treatment regimens.

To ensure accuracy of FVIII trough/peak (recovery) and inhibitor testing, subjects following a prophylaxis regimen should schedule clinic visits 48 hours after the previous dose of rFVIII Fc, whenever possible.

CONFIDENTIAL

The information contained herein may not be used, disclosed, or published without the written consent of Biogen Idec MA Inc.

Subjects first dosed with rFVIII Fc when <12 years of age will be followed to at least 100 EDs, even if rFVIII Fc becomes commercially available.

All subjects will have the opportunity to continue in this study for up to 4 years or until rFVIII Fc is commercially available in the applicable participating country.

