5.1.1. Description of Study Days

Definition of Gap

A gap is calculated as:

Date of Visit 1 for study 8HA01EXT – date of the last day of the parent study,

where the last day of the parent study is defined as either 1) the date of the last rFVIII Fc dose for subjects on a prophylactic regimen in study 997HA301, 8HA02PED, 997HA307, or 997HA309, or only had PK injections in study 997HA307 or 997HA309, or 2) the date of the last non-safety follow-up study visit for subjects on the episodic regimen in study 997HA301 or 997HA307 or

subjects who ended the study in a surgical/rehabilitation period in study 997HA301, 8HA02PED, 997HA307, or HA997309.

A listing will be provided for subjects from studies 997HA301, 997HA307 and 997HA309 who had a gap of greater than 7 days and subjects from study 8HA02PED who had a gap of greater than 4 days. These gaps were identified because for the majority of the subjects, the FVIII activity is below 1% after 7 days for subjects from studies 997HA301 997HA307, and 997HA309 and below 1% after 4 days for subjects from study 8HA02PED. In addition, the definition of Study Day 1 will be somewhat different for these subjects with a longer gap, as described below.

For simplicity, the gap of greater than 7 days for subjects from studies 997HA301, 997HA307, and 997HA309 and the gap of greater than 4 days for subjects from study 8HA02PED will be referred to as the gap of greater than 7 or 4 days.

Definition of 8HA01EXT Study Day 1

8HA01EXT Study Day 1 will be used as a reference date to calculate the study day relative to the start of study 8HA01EXT. The definition of 8HA01EXT Study Day 1 depends on the length of the gap.

For 8HA01EXT subjects with no gap or a gap of less than or equal to 7 or 4 days:

In general, 8HA01EXT Study Day 1 is defined as the last day of the parent study, i.e. either 1) the day of the last rFVIII Fc dose for subjects on a prophylactic regimen in study 997HA301, 8HA02PED, 997HA307, or 997HA309, or 2) the day of the last non-safety follow-up study visit for subjects on the episodic regimen in study 997HA301 or 997HA307 or subjects who ended the study in a surgical/rehabilitation period in study 997HA301, 8HA02PED, 997HA307, or 997HA309.

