For subjects from studies 997HA307 and 997HA309 who only had PK injections (i.e. no injections in treatment phase) and enroll in 8HA01EXT on a prophylactic regimen, the 8HA01EXT Study Day 1 is either 1) the day of the first study visit if there is a prophylactic dose on that day, or 2) the day of the last non-safety follow-up study visit in studies 997HA307 and 997HA309 if there is no prophylactic dose on the day of the first study visit in 8HA01EXT.

For 8HA01EXT subjects with a gap of greater than 7 or 4 days:

8HA01EXT Study Day 1 is defined as either 1) the date of the first rFVIII Fc dose in study 8HA01EXT for subjects on a prophylactic regimen at the start of study 8HA01EXT, or 2) the day of the first study visit for subjects starting study 8HA01EXT on the episodic regimen or in a surgical/rehabilitation period.

Definition of Study Day

The following definition of Study Day will be used in the analysis:

- 8HA01EXT Study Day: day relative to 8HA01EXT Study Day 1, as defined above.

The start/stop day of events will be calculated as (date of event – date of Study Day 1 + 1) if the date of the event is on or after the Study Day 1 date, or (date of event – date of Study Day 1) if the date of the event is before the Study Day 1 date. Study Day -1 is the day immediately preceding Study Day 1. There is no Study Day 0 in this study.

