- For subjects who were on the episodic treatment arm in study 997HA301 or 997HA307, or only had PK injections in study 997HA307 or 997HA309, and started study 8HA01EXT on the episodic regimen, if there was any dose on 8HA01EXT Study Day 1, then the episodic treatment regimen in study 8HA01EXT will start at the time of that dose.
- For subjects who were on the episodic treatment arm in study 997HA301 or 997HA307 and switched to a prophylactic regimen at study 8HA01EXT start, and had a gap of less than 7 days:
 - If there was no prophylactic dose on the last non-safety follow-up study visit, then the prophylactic treatment regimen in study 8HA01EXT will start at the time of the first prophylactic dose in study 8HA01EXT. The interval from the starting time on 8HA01EXT Study Day 1 (i.e., 23:59 on the day of the last non-safety follow-up study visit) through 1 minute before the first prophylactic dose in study 8HA01EXT will be imputed as the episodic treatment regimen in study 8HA01EXT.
 - If there was a prophylactic dose on the last non-safety follow-up study visit, then the start of the prophylactic regimen in study 8HA01EXT will be the time of that prophylactic dose. In this case, the time from the start of the prophylactic regimen to 23:59 on that day, i.e. the end of the episodic regimen in studies 997HA301 and 997HA307, will be attributed to both study 997HA301/997HA307 and study 8HA01EXT. If there were bleeding episodes during this overlap of time, they would have been attributed to studies 997HA301 and 997HA307.

The end of the last treatment regimen (for subjects who have not changed treatment regimens, it will be the same treatment regimen as they started) will be either 1) the date and time of the last rFVIII Fc dose for subjects whose last treatment regimen was prophylactic or if they were in a surgical/rehabilitation period in study 8HA01EXT, or 2) 23:59 on the day of the last non-safety follow-up study visit for subjects whose last treatment regimen in study 8HA01EXT was episodic.

Treatment Regimen Changes

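### SAP 5.1 names Visit 1 as the Baseline Visit, yet its own date rule makes Visit 1 post-baseline for parent-prophylaxis subjects with a gap of 1 to 7 days (1 to 4 for 8HA02PED)

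*SAP*

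**What the plan says.** Three statements in SAP 5.1 (General Principles) bear on this:

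- Baseline is the last usable non-missing measurement "taken prior to or on the date of 8HA01EXT study Study Day 1".
- Subjects enrol at the EOT visit of the parent study, "which will serve as the Baseline Visit for this extension study (Visit 1".
- "Post-baseline values are defined as any assessment taken after 8HA01EXT Study Day 1".

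SAP 5.1.1 (Description of Study Days) defines the gap as the Visit 1 date minus the last day of the parent study. For "subjects with no gap or a gap of less than or equal to 7 or 4 days" it sets Study Day 1 at that last parent day. For subjects treated prophylactically in the parent study, this is "the day of the last rFVIII Fc dose for subjects on a prophylactic regimen", not the EOT visit. The 7-day limit applies to 997HA301, 997HA307 and 997HA309, and the 4-day limit to 8HA02PED. Above the limit, Study Day 1 moves to the first extension dose, or to the first study visit for subjects who start episodic or in a surgical/rehabilitation period.

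The baseline rule carries a general exception clause, but SAP 7.4.4 (joint score), 7.5 (patient-reported outcomes) and 8.3 (laboratory) refer back to 5.1 without making any exception.

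**The concern.** The named Baseline Visit and the date rule agree only if Visit 1 is on or before Study Day 1. For parent-prophylaxis subjects with a short positive gap, Study Day 1 is anchored to a dose given before the visit, so the two rules disagree. Two programmers could derive different baselines from the same paragraph.

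Where the EOT visit is Visit 1, following the date rule has four effects:

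- Baseline falls back to an earlier parent-study value or is missing. A subject with no earlier usable value leaves the change-from-baseline summaries, because SAP 5.1.2 requires both a baseline and a post-baseline value.
- Visit 1 laboratory values enter the post-baseline minimum and maximum behind the shift tables (SAP 8.3.1.2).
- Visit 1 values can count as post-baseline abnormalities (SAP 8.3.1.3).
- In the antibody table (SAP 8.3.3), a subject first positive at Visit 1 can stay in the baseline-negative denominator and count as positive after Study Day 1, although the sample followed parent-study treatment only.

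**Working it through.** No published figure needs reproducing; the check is date arithmetic.

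**Inputs.** Gap = Visit 1 date − last parent day (SAP 5.1.1). Study day = date − Study Day 1 date + 1 for dates on or after Study Day 1, with no Day 0 (SAP 5.1.1). The branch examined is parent prophylaxis, excluding PK-only subjects (who have their own Study Day 1 rule) and subjects who ended the parent study in a surgical/rehabilitation period (whose last parent day is a visit).

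**Formula.** At or below the cut-off, Study Day 1 = last parent dose date. So the study day of Visit 1 = (Visit 1 date − last parent dose date) + 1 = gap + 1.

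| Gap (days) | Visit 1, 997HA301/307/309 | Visit 1, 8HA02PED |
|---|---|---|
| 0 | Day 1: baseline-eligible | Day 1: baseline-eligible |
| 1 to 4 | Days 2 to 5: post-baseline | Days 2 to 5: post-baseline |
| 5 to 7 | Days 6 to 8: post-baseline | above cut-off: eligible* |
| 8 or more | above cut-off: eligible* | above cut-off: eligible* |

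*For subjects who start the extension on prophylaxis, provided the first extension dose is on or after Visit 1. For those who start episodic or in a surgical/rehabilitation period, Study Day 1 is the first study visit itself.

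The role of the same visit therefore changes twice as the gap grows. The cut-offs come from when FVIII activity falls below 1% (SAP 5.1.1), which concerns continuity of dosing and has no bearing on whether a visit is a baseline.

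**Separate EOT visit.** Suppose EOT was an earlier visit on the last-dose day and Visit 1 came later. The EOT values are then on Study Day 1 and remain a valid baseline. Protocol footnote 1 to the Screening and Treatment Period says EOT tests need not be repeated at Visit 1, so only assessments actually done at the later visit become post-baseline. That situation is not specific to parent-prophylaxis subjects: anyone whose Study Day 1 is the last parent visit and whose Visit 1 follows some days later is in the same position.

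**How many.** Planned sizes are 144 + 50 + 12 + 8 = 214 (SAP 3.3.1), and the branch is a subset of these. The documents give no gap distribution. The planned gap listing covers only gaps above 7 (4) days, so it would not reveal the affected subjects.

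**The case against.** The strongest reply is that anchoring Study Day 1 to the last parent dose is deliberate. SAP 5.3.1 starts the extension regimen one minute after that dose, SAP 5.3.4 starts the safety period on that day, and SAP 8.2.2 treats adverse events from then on as extension events regardless of the gap. On that view, data collected after the dose are extension data, antibody results included. This stands as a reason to keep Study Day 1 for those purposes. It does not reconcile the Baseline Visit sentence with the date rule.

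It is also fair that the consequences may be slight. Entrants completed a parent study, and the joint score and questionnaires are done only if they were done there, so an earlier value will often exist. The shift and abnormality tables keep subjects without a baseline (SAP 8.3.1.2 and 8.3.1.3).

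A reader might infer that most parent-prophylaxis subjects are affected. The argument would run as follows. Protocol 7.1 says these subjects "should schedule clinic visits 48 hours after the previous dose". If the dose given at the EOT visit belongs to the extension, the last parent dose was 2 days earlier, the gap is 2 and Visit 1 is Study Day 3. Two SAP rules do take a visit-day dose as the extension start: 5.1.1 for PK-only subjects ("the day of the first study visit if there is a prophylactic dose on that day") and 5.3.1 for parent-episodic subjects switching to prophylaxis ("then the start of the prophylactic regimen in study 8HA01EXT will be the time of that prophylactic dose").

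The documents do not support that inference. Neither of those groups had a parent prophylactic regimen to which the dose could belong. For a parent-prophylaxis subject, an EOT-day dose can as naturally be the last parent dose, giving gap 0 and no conflict; the SAP does not say which applies. The 48-hour timing is an extension instruction to be followed where possible, and its use at the parent EOT visit would be an assumption.

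**Conclusion.** The contradiction is real and follows from the text. For subjects on prophylaxis in the parent study (not PK-only, and not ending in a surgical/rehabilitation period) with a gap of 1 to 7 days, or 1 to 4 for 8HA02PED, the named Baseline Visit is post-baseline. The date arithmetic is certain. How many subjects it touches is not: the number is unknown and may be small, and the documents give no basis for an effect size.

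The severity is minor. Only descriptive change, shift, abnormality and antibody tables are affected, and Protocol Section 16 plans no hypothesis tests. A reader might infer that the primary safety result or the bleeding rates are compromised. They are not: the inhibitor listing, annualized bleeding rate, exposure and consumption do not use this baseline. Nor should one conclude that every short-gap subject loses his EOT baseline. That happens only when the EOT visit and Visit 1 are the same visit.

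**What to change.** In SAP 5.1:

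- Define baseline as the last non-missing value on or before the later of Study Day 1 and the Visit 1 date. If Visit 1 spans several clinic dates, which Protocol footnote 1 allows, use the last of them.
- Define post-baseline as any assessment after that date.

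Use the same cut for both the denominator and the positivity count in SAP 8.3.3. Keep Study Day 1 for all other purposes. Report the number of subjects with a gap of 1 to 7 (1 to 4) days next to the planned listing of longer gaps.

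A cut tied to the first extension dose would be a poor substitute. For episodic subjects that dose may be their first treated bleed, possibly months after Visit 1.

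The cost is a change of wording in two SAP sections, one derivation change and one count, with no new data. The downside is that in these subjects the adverse event cut and the laboratory, patient-reported outcome and antibody cut will differ by up to 7 (4) days. A footnote should say so.

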5.1.1. Description of Study Days

Definition of Gap

A gap is calculated as:

Date of Visit 1 for study 8HA01EXT – date of the last day of the parent study,

where the last day of the parent study is defined as either 1) the date of the last rFVIII Fc dose for subjects on a prophylactic regimen in study 997HA301, 8HA02PED, 997HA307, or 997HA309, or only had PK injections in study 997HA307 or 997HA309, or 2) the date of the last non-safety follow-up study visit for subjects on the episodic regimen in study 997HA301 or 997HA307 or

subjects who ended the study in a surgical/rehabilitation period in study 997HA301, 8HA02PED, 997HA307, or HA997309.

A listing will be provided for subjects from studies 997HA301, 997HA307 and 997HA309 who had a gap of greater than 7 days and subjects from study 8HA02PED who had a gap of greater than 4 days. These gaps were identified because for the majority of the subjects, the FVIII activity is below 1% after 7 days for subjects from studies 997HA301 997HA307, and 997HA309 and below 1% after 4 days for subjects from study 8HA02PED. In addition, the definition of Study Day 1 will be somewhat different for these subjects with a longer gap, as described below.

For simplicity, the gap of greater than 7 days for subjects from studies 997HA301, 997HA307, and 997HA309 and the gap of greater than 4 days for subjects from study 8HA02PED will be referred to as the gap of greater than 7 or 4 days.

Definition of 8HA01EXT Study Day 1

8HA01EXT Study Day 1 will be used as a reference date to calculate the study day relative to the start of study 8HA01EXT. The definition of 8HA01EXT Study Day 1 depends on the length of the gap.

For 8HA01EXT subjects with no gap or a gap of less than or equal to 7 or 4 days:

In general, 8HA01EXT Study Day 1 is defined as the last day of the parent study, i.e. either 1) the day of the last rFVIII Fc dose for subjects on a prophylactic regimen in study 997HA301, 8HA02PED, 997HA307, or 997HA309, or 2) the day of the last non-safety follow-up study visit for subjects on the episodic regimen in study 997HA301 or 997HA307 or subjects who ended the study in a surgical/rehabilitation period in study 997HA301, 8HA02PED, 997HA307, or 997HA309.

For subjects from studies 997HA307 and 997HA309 who only had PK injections (i.e. no injections in treatment phase) and enroll in 8HA01EXT on a prophylactic regimen, the 8HA01EXT Study Day 1 is either 1) the day of the first study visit if there is a prophylactic dose on that day, or 2) the day of the last non-safety follow-up study visit in studies 997HA307 and 997HA309 if there is no prophylactic dose on the day of the first study visit in 8HA01EXT.

For 8HA01EXT subjects with a gap of greater than 7 or 4 days:

8HA01EXT Study Day 1 is defined as either 1) the date of the first rFVIII Fc dose in study 8HA01EXT for subjects on a prophylactic regimen at the start of study 8HA01EXT, or 2) the day of the first study visit for subjects starting study 8HA01EXT on the episodic regimen or in a surgical/rehabilitation period.

Definition of Study Day

The following definition of Study Day will be used in the analysis:

- 8HA01EXT Study Day: day relative to 8HA01EXT Study Day 1, as defined above.

The start/stop day of events will be calculated as (date of event – date of Study Day 1 + 1) if the date of the event is on or after the Study Day 1 date, or (date of event – date of Study Day 1) if the date of the event is before the Study Day 1 date. Study Day -1 is the day immediately preceding Study Day 1. There is no Study Day 0 in this study.

